2.8 Statistical Analysis

The primary outcome is a live birth resulting from a pregnancy that is conceived within the 6 months from initiation of treatment. Live birth is defined as a delivery of a live infant after 20-weeks gestation. Secondary outcomes include pregnancy, defined by a positive home pregnancy test within the 6 months of treatment. We will conduct an intent-to-treat analysis. Cumulative incidence of live birth and pregnancy will be compared between those couples randomized to antioxidants and those couples randomized to placebo. In addition, discrete-time hazard models will be used to compare time-to-pregnancy between the two treatment groups. Subsequent subgroup analyses will be conducted to assess for effect modification by type of baseline sperm abnormality (asthenospermia, high DNA fragmentation, oligospermia).

After transformations, if needed, semen parameter measures will be analyzed using a generalized linear mixed model (including random effects for site if necessary) or generalized linear model (if fixed effects for site are used). Interaction terms will be used to determine the

extent to which the change in semen parameter measures differs by type of baseline sperm abnormality (asthenospermia, high DNA fragmentation, oligospermia). If there is evidence of effect modification, change estimates will be determined for each type of baseline sperm abnormality.

For the power analysis, we assume live birth rates of 35% in the antioxidant group and 25% in the control group, and 17% drop-out. Under these assumptions, the power by using a two-sided chi square test at $\alpha=0.05$ would be 0.80.

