5.2 Study Population

5.2.1 Inclusion Criteria

Couple

- 12 or more months of infertility (primary or secondary) for couples with female partner under 35. 6 or more months of infertility (primary or secondary) for couples with female partner 35 years of age or older.
- Heterosexual
- Cohabiting and able to have regular intercourse

Male:

- ≥ 18 years of age
- At least one abnormal semen parameter on a semen analysis within the past 6 months:
 - Sperm concentration ≤ 15 Million/ml
 - Total motility $\leq 40\%$
 - Normal morphology (Kruger) $\leq 4\%$
 - DNA fragmentation (SCSA, DNA fragmentation index) $>25\%$

Female:

- ≥ 18 years of age and ≤ 40 years of age
- For women ≥ 35 years of age, evidence of normal ovarian reserve as assessed by menstrual cycle day 3 (+/-2 days) FSH ≤ 10 IU/L with estradiol ≤ 70 pg/mL, AMH ≥ 1.0 ng/mL, OR antral follicle count >10 within one year prior to study initiation.
- Evidence of at least one patent fallopian tube as determined by an HSG or laparoscopy showing at least one patent fallopian tube or a saline infusion sonogram showing spillage of contrast material. OR An uncomplicated intrauterine non-IVF pregnancy and uncomplicated delivery and postpartum course resulting in live birth within the last three years will also serve as sufficient evidence of a patent tube and normal uterine cavity as long as the subject did not have, during the pregnancy or subsequently, risk factors for Asherman's syndrome or tubal disease or other disorder leading to an increased suspicion for intrauterine abnormality or tubal occlusion.
- Regular cycles defined as ≥ 25 days and ≤ 35 days in duration
- Evidence of ovulation including biphasic basal body temperatures, positive ovulation predictor kits, or progesterone level ≥ 3 ng/ml.

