6. Schedule study visit 3 for ≤ 60 days. Provide semen collection instructions for next visit.
7. Provide male with 14 ovulation strips and 4 pregnancy tests.

5.7.4 *Study treatment visit 3 (males only):*

1. Participant completes the ASA24 online.

2. Count remaining pills.
3. Assess for side effects from treatment.
4. Collect blood sample
 - a. Collect serum for UVA central laboratory for measurement of vitamin D 25-OH.
 - b. Collect and store serum. Randomly selected samples will be shipped to a central laboratory for analysis of antioxidant levels.
5. Obtain a semen sample following appropriate abstinence and evaluate by semen analysis as suggested by WHO 5 standards.
 - a. Samples will be evaluated for volume, sperm concentration, percent sperm motility, forward progressive motility at the local site laboratory.
 - b. Prepare semen slides. Incidence of normal sperm morphology will be determined using Kruger Strict morphological assessment by a single technician at a central laboratory.
 - c. Three aliquots of raw semen will be frozen, stored at -20° C, and then shipped in batches to a central site for TUNEL, SCSA, and COMET assay.
6. Dispense assigned study pill kit. Instruct participant to take one capsule and one tablet twice a day. Provide 3-month supply (Package 3). Instruct male to have female partner call with menses to schedule baseline ultrasound for clomiphene citrate/IUI cycle.
7. Dispense patient journal.
8. Schedule study visit 4 for ≤ 120 days. Instruct participant to bring pill bottles with any remaining pills with him on day of next visit.

5.7.5 *Clomid and IUI cycles (couple):*

Baseline Ultrasound Visit

1. Females will call with menses and come in Day 1-5 (Preferably day 3 for baseline monitoring) for first cycle only.
2. Perform comprehensive baseline ultrasound.
3. Dispense Infertility Treatment Medications: 10 tablets of clomiphene citrate and 10,000 IU hCG. Patient is to take clomiphene citrate 100 mg for 5 days starting on cycle days 1,2,3,4 or 5.
4. Dispense patient journal

Monitoring Visit number 1: Within 3 days after completing 5-day drug cycle (Cycle Day 8-12)

1. Transvaginal ultrasound for endometrial and follicular monitoring
2. Adverse effects and concomitant medications query

Monitoring Visit number 2 and beyond:

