Visits for subjects will be conducted on an individualized basis until hCG administration. When a decision has been made to give hCG on the next day, a follow up monitoring visit on that day is unnecessary.

- Transvaginal ultrasound examination for endometrial and follicular monitoring
- Adverse effects and concomitant medications query

hCG administration day:

1. 10,000 IU in 1 cc diluent delivered IM
2. Transvaginal ultrasound examination for endometrial and follicular monitoring is not necessary if one has been performed within 2 days.

Criteria for hCG administration:

- First occurrence of lead follicle reaching 20 mm (in average diameter in two dimensions), or
 - First occurrence of two lead follicles greater than 18 mm diameter (in average diameter in two dimensions), or
- The day after the lead follicle reaching 18 mm (in average diameter in two dimensions), or the day of detection of presumptive ovulation by ultrasound

Criteria for withholding hCG:

- If a leading follicle does not reach a mean diameter of 18 mm after 18 days of treatment, or
- Endogenous LH surge happens [which can lead to premature luteinization], or
- Increased risk for OHSS and/or high-order multiple gestational pregnancy exists when more than 4 growing follicles develop (mean diameter >18 mm), or

**Protocol medication adjustment:*

1. If no ovulation or development of at least one follicle ≥ 18 mm in average diameter, then increase dosage in the subsequent cycle.
2. If only one follicle ≥ 18 mm in average diameter, the dosage increase for subsequent cycles will be left to physician's discretion.
3. If more than four follicles are ≥ 18 mm in average diameter, dosage will be reduced in the subsequent cycle.

**Cancellation criteria:* Cycles will be cancelled if significant adverse reactions develop in response to administered medications, if criteria for withholding hCG administration are encountered, or per patient's request.

Insemination day visit:

1. Each site will perform its standard sperm processing and intrauterine insemination procedure.
2. Record parameters of semen analysis before and after sperm preparation.
3. Record time of insemination.
4. Instruct patient to check urine pregnancy test 2 weeks after insemination and call with results.
5. Provide clomiphene citrate for next cycle. Counsel not to take it until instructed to do so.

Pregnancy test: Patient is to do a home pregnancy test 2 weeks after insemination using the urine home pregnancy tests provided.

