Four possible outcomes:

- A. No pregnancy on urine pregnancy test
- B. Positive urine pregnancy test- serum β hcg level returns <5 mIU/ml- no pregnancy
- C. Positive urine pregnancy test- serum β hcg level returns >5 mIU/ml, retest for rising level in 2 days- no pregnancy
- D. Positive urine pregnancy test- serum β hcg level returns >5 mIU/ml, retest for rising level in 2 days- pregnancy

A. Negative Urine Pregnancy Test/No pregnancy: *Repeat cycles until pregnancy occurs or male completes a total of 6 months of treatment.*

Criteria to initiate Cycles 2 or 3 (Day 3 +/- 2 days):

1. Negative urine pregnancy test,
2. Male still on treatment.

Cycle 2 and 3 will be identical to Cycle 1, except that there will be no Baseline Ultrasound visit. When the subject contacts the site with the results of her urine pregnancy test or start of menses, she will be instructed by the site to start her clomiphene citrate. She will then return to the site for Monitoring Visit 1 (see above).

In women who report a positive urine pregnancy test, obtain serum β hcg level.

B & C. Positive Urine Pregnancy Test (no pregnancy)

Patient will have a serum β hcg level checked. If >5 mIU/ml, return in 2 days to check for a rising level in serum β hCG; if the first level is <5 mIU/ml or if there is not a rising level, patient will initiate Cycles 2 or 3.

D. Positive Urine Pregnancy Test (pregnancy): *Biochemical pregnancy will be defined as β hCG >5 units/ml 2 weeks after insemination followed by a rising level two days later*

- Patient will have a serum β hcg level checked. If >5 mIU/ml, patient will return in 2 days to check a rising level in serum β hCG.
- If rising β hcg level, schedule Pregnancy Ultrasound Visit. Instruct male to come to pregnancy ultrasound visit to complete study visit 4. Remind him to bring his pill bottle.

5.7.6 *Study visit 4 (males only):*

1. Count remaining pills.
2. Confirm pregnancy status (pregnant or not pregnant) of female partner.
3. Assess for side effects from treatment.
4. Obtain blood sample from those males whose female partner did not conceive.
 - a. Collect and store serum. Randomly selected samples will be shipped to a central laboratory for analysis of antioxidant levels.

5.7.7 *Pregnancy ultrasound(s):*

To be done between 6 and 9 weeks gestation. Clinical pregnancy rate will be defined as the identification of intrauterine sac(s) with positive fetal cardiac activity in at least one sac.

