7.2 Primary and Secondary Outcomes

The primary outcome is a live birth resulting from a pregnancy occurring within the 6 months of treatment. Live birth is defined as a delivery of a live infant after 20-weeks gestation. Secondary outcomes include pregnancy, defined by a positive home pregnancy test within the 6 months of treatment. We will conduct an intent-to-treat analysis. Cumulative incidence of live birth and pregnancy will be compared between those couples randomized to antioxidants and those couples randomized to placebo. In addition, discrete-time hazard models will be used to compare time-to-pregnancy between groups. Subsequent subgroup analyses will be conducted to assess for effect modification by type of baseline sperm abnormality. All analyses will include fixed or random effect terms as needed to account for potential site effects.

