7.3 Sample Size and Statistical Power

For the power analysis, we assume live birth rates of 35% in the antioxidant group and 25% in the control group, and 17% drop-out (based on drop-out rate in prior RMN trials). A 25% live birth rate was estimated, assuming 5% live birth rate in the first 3 months of timed intercourse and a 20% live birth rate in the 3 clomid/IUI cycles. The 20% live birth rate is the live birth rate in AMIGOS participants receiving up to 3 cycles of clomid/IUI and female partner under the age of 35. Under these assumptions, a sample size of 395 per group will yield 80% power using a two-sided chi square test at $\alpha=0.05$ (Table 2).

Table 2: Sample size estimates under a variety of assumptions

Proportion (%) of live birth in placebo group	Proportion (%) of live birth in antioxidant group	Power (%)	Number of patients per arm with 0% dropout	Total number of patients with 0% dropout	Total number of patients with 17% dropout
20	30	80	294	588	708
20	30	90	392	784	944
25	35	80	328	656	790
25	35	90	440	880	1060
30	40	80	356	712	858
30	40	90	477	954	1150
20	35	80	138	276	332
20	35	90	185	370	446
25	40	80	152	304	366
25	40	90	203	406	490

For subgroup analyses, power is dependent on the distribution of the sperm abnormalities, the control live birth rate and the treatment effect difference (see Table 3).

Table 3: Power for subgroup analyses

Proportion affected (%)	Total N for subgroup	Control Group Pregnancy Proportion (%)	Treatment Effect Difference (%)	Alpha	Power (%)
70	552	20	10	0.05	78
60	474	20	10	0.05	71
50	394	20	10	0.05	63
40	316	20	10	0.05	54
30	236	20	10	0.05	43
70	553	20	15	0.05	98
60	474	20	15	0.05	96
50	395	20	15	0.05	92
40	316	20	15	0.05	85
30	237	20	15	0.05	74
70	553	25	15	0.05	97

60	474	25	15	0.05	94
50	395	25	15	0.05	89
40	316	25	15	0.05	82
30	237	25	15	0.05	69

8 Technical Aspects

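### Live birth is dated by conception but pregnancy by a home test, so a late third IUI cycle can give a counted birth with no counted pregnancy

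*Combined protocol and SAP*

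**What the plan says.** Section 2.8 defines the primary outcome as "a live birth resulting from a pregnancy that is conceived within the 6 months from initiation of treatment". Section 7.2 repeats this but requires the pregnancy to occur, rather than be conceived, in the 6 months. Both sections then define the secondary outcome as "pregnancy, defined by a positive home pregnancy test within the 6 months of treatment". Sections 2.5 and 4.1 are looser: they refer to live birth after as much as 6 months of treatment and set no last date for conception.

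The schedule is in sections 5.6 and 5.7. Visits 2 and 3 fall by days 30 and 90. Package 3, given at visit 3, holds 90 days of drug. At visit 3 the instruction is: "Instruct male to have female partner call with menses to schedule baseline ultrasound for clomiphene citrate/IUI cycle". Up to three clomid/IUI cycles follow, and in each one "Patient is to do a home pregnancy test 2 weeks after insemination". Cycles 2 and 3 require a negative test and "Male still on treatment". For the male's last visit, section 5.7.4 says "Schedule study visit 4 for ≤ 120 days". Eligible women have "Regular cycles defined as ≥ 25 days and ≤ 35 days in duration" (section 5.2.1). Section 7.3 builds the 25% control rate from 5 points in the first 3 months and "a 20% live birth rate in the 3 clomid/IUI cycles".

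**The concern.** The condition on the male being on treatment limits when cycle 3 starts. It does not limit when its insemination or test takes place. A couple can therefore follow the protocol exactly, be inseminated just before month 6, and test positive just after it. Under sections 2.8 and 7.2 a resulting live birth counts, while the pregnancy that led to it does not.

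This affects interpretation. Readers expect live births to be a subset of pregnancies. Here the two cumulative rates would rest on different sets of couples, and the pregnancy rate would be too low in both arms. Time to pregnancy has the same problem if its event is the counted positive test. A second gap concerns third inseminations after month 6: section 2.8 excludes their births, while sections 2.5 and 4.1 could include them.

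**Working it through.** **The plan's own figure.** For 25% versus 35%, two-sided alpha 0.05, 80% power, pooled variance and no continuity correction: n = [1.96·√(2·0.30·0.70) + 0.8416·√(0.25·0.75 + 0.35·0.65)]² / 0.10² = 328.5, so 329 per arm (stated 328). Then 656/0.83 = 790.4 (stated 790). Power at 328 per arm is 79.9%. The sample size reproduces and is not in dispute.

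**Timing inputs from the documents.** Visit 3 by day 90; first cycle starts at the next menses; up to three cycles; test 14 days after insemination; cycle 3 started on treatment.

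**Assumptions not in the documents.** Insemination on cycle day d = 14; next cycle 14 days later (28-day cycles); wait W from visit 3 to menses uniform over 0 to 28 days; no skipped or cancelled cycle; 6 months = 180 days.

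**Formulas, in days after visit 3.**
- Cycle 3 starts at W + 2(d + 14) = W + 56, at most 84, so it can always start on treatment.
- Third insemination: W + 3d + 28 = W + 70, at most 98.
- Third test: W + 3d + 42 = W + 84, at most 112.

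With R days left between visit 3 and day 180, the insemination is late if W > R − 70 and the test is late if W > R − 84.

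| Visit 3 | R | Insemination after day 180 | Test after day 180 | Insemination in time, test late |
|---|---|---|---|---|
| Day 90 | 90 | 8/28 = 29% | 22/28 = 79% | 14/28 = 50% |
| Day 85 | 95 | 3/28 = 11% | 17/28 = 61% | 14/28 = 50% |
| Day 80 | 100 | 0% | 12/28 = 43% | 12/28 = 43% |

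**Sensitivity, visit 3 on day 90.**
- 25-day cycles: 0% of inseminations and 40% of tests late.
- 30-day cycles: 53% of inseminations and essentially all tests late.
- 28-day cycles, if a menses up to 4 days before visit 3 can be used (section 5.7.5 lets women come in on days 1 to 5): 14% and 64%.
- 28-day cycles with 6 months taken as 183 days: 18% and 68%.

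**Size in the control arm.** With equal per-cycle success, 20% over three cycles gives 1 − 0.8^(1/3) = 7.17% per cycle. Cycle 3 then contributes 0.8^(2/3) × 7.17% = 6.18 of the 20 points. The last column of the table gives 0.43 × 6.18 = 2.7 to 0.50 × 6.18 = 3.1 points of live birth with no counted pregnancy. Among 328 control couples that is about 9 to 10 births, out of 328 × 0.25 = 82.

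**The case against.** The strongest reply is that the problem depends on a literal reading of one sentence, which appears in both 2.8 and 7.2. Section 4.2 defines pregnancy as a positive test with no date limit. Section 5.7.5 confirms IUI pregnancies by rising serum hCG, also with no cut-off. Site staff would probably record a positive test in month 7, and pregnancies are followed to outcome, so no data are lost. This stands as far as it goes: the data will exist. But 2.8 and 7.2 are the analysis text, and they contain the only dated rule for pregnancy. Leaving the choice until data are in hand is what a plan should prevent.

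The percentages are also fairly said to be assumption-driven. Day 90 is the latest scheduled visit 3, and an earlier visit or a usable recent menses reduces them. That is why a range is given. The mismatch itself does not depend on them, because the test always follows insemination by 2 weeks.

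Limiting conception to the treatment period is a defensible choice, and three cycles were never guaranteed. That is accepted. The point is only that the same limit should apply to both outcomes. Nor do the documents tie a miscarriage denominator to the home-test date, so distortion of the miscarriage rate is possible but not shown.

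**Conclusion.** The mismatch is real and follows from the text. Under the stated assumptions, 43% to 79% of third-cycle tests fall after day 180 for visit 3 on day 80 to 90, and 43% to 50% of third cycles combine a timely insemination with a late test. Third inseminations after day 180 range from 0% to 29%, with more for longer cycles and fewer if a recent menses can be used. Their status is unclear across 2.5, 2.8, 4.1 and 7.2.

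Three stronger readings are tempting, but the documents do not support them.
- **Power is lost.** A reader might infer that uncounted births cut power to about 76%. That takes visit 3 on day 90, the strict wording of 2.8 and a constant ratio of 1.4. The plan states no constant ratio, and its Table 2 is built on absolute differences. With a 10-point difference held, power at 328 per arm stays at 80% to 82%.
- **The comparison is biased.** The timing rules apply alike to both arms of a blinded trial, so nothing points to between-arm bias.
- **The 120-day window is the error, or covers every third test.** It schedules the male's visit 4 and is not an outcome rule. It covers every third test at 28-day cycles (latest day 112). A 35-day cycle started on day 90 after visit 3 is tested on day 90 + 35 = 125.

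**What to change.** In sections 2.8 and 7.2, date pregnancy and time to pregnancy by conception within 6 months of starting treatment, whatever the test date. This is the same window as live birth. For IUI cycles, use the insemination date, which section 5.7.5 already requires sites to record.

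Add one sentence stating whether a conception after month 6 counts when it comes from a study cycle started on treatment. Apply that answer to every outcome, align sections 2.5 and 4.1 with it, and report the number of such inseminations by arm. Either answer is defensible.

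The cost is a small wording change, best made before outcome data by arm are seen. Visits, drug supply, randomisation and sample size stay as they are. If late study cycles are counted, some counted inseminations fall after the last dose. With visit 3 on day 90, the longest delay is 98 − 90 = 8 days at 28-day cycles and 106 − 90 = 16 days at 30-day cycles. It reaches 21 days in the extreme case of a 35-day cycle started on the last treatment day (insemination on cycle day 35 − 14 = 21).

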4.2 Secondary Aim

We will assess secondary outcomes including cumulative pregnancy rates with pregnancy defined as a positive pregnancy test, clinical pregnancy rates defined as presence of a fetus with cardiac activity, miscarriage rate, defined as the loss of a pregnancy prior to 20-weeks gestation, and time to pregnancy. In addition, we will examine changes in semen parameters and DNA fragmentation at 3 months of treatment.

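### The secondary pregnancy outcome counts every positive home test, including IUI-cycle positives that section 5.7.5 classes as no pregnancy after serum hCG

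*Combined protocol and SAP*

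**What the plan says.** Section 7.2, with the same sentence in 2.8, sets the outcome: "Secondary outcomes include pregnancy, defined by a positive home pregnancy test within the 6 months of treatment". Section 4.2 is looser about the type of test: "cumulative pregnancy rates with pregnancy defined as a positive pregnancy test". None of the three mentions serum confirmation. Section 7.2 then uses pregnancy in two planned comparisons, cumulative incidence and a discrete-time hazard model for time to pregnancy. Section 4.2 adds a "miscarriage rate, defined as the loss of a pregnancy prior to 20-weeks gestation".

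Section 5.7.5, which governs the clomiphene/IUI cycles in months 4–6, requires serum hCG after a positive home urine test. Its heading for two of the four possible results is "B & C. Positive Urine Pregnancy Test (no pregnancy"), and the action is: "if the first level is <5 mIU/ml or if there is not a rising level, patient will initiate Cycles 2 or 3". Only result D, a level above 5 that has risen two days later, is called a pregnancy and leads to the ultrasound. The same section gives its own definition of biochemical pregnancy, which also requires a rising level.

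For months 1–3 the documents describe only home testing at missed menses (5.1), with a positive test leading to scheduling of the ultrasound (5.7.1). No serum step is written for that period.

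**The concern.** A programmer following 7.2 and a clinician following 5.7.5 would classify the same couple in opposite ways. This is more than missing detail. The rule in 7.2 can be programmed, and for B and C couples it gives a result that the trial's own procedure contradicts.

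Three secondary results are exposed. The cumulative pregnancy rate gains events. In the time-to-pregnancy model a B or C couple has its event, and leaves the risk set, at a cycle after which it goes straight on to another insemination. If that couple then conceives, the conception is dated too early. The miscarriage rate depends on which positives count as pregnancies. If the choice is left until the data are in hand, it becomes a post hoc decision about an outcome definition.

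**Working it through.** **The plan's own figures.** The plan states no figure for the pregnancy outcome. Section 7.3 sizes the trial on live birth: 25% against 35%, 80% power, two-sided 0.05. The usual two-proportion formula without continuity correction gives 329 per arm (stated 328), and power with 328 is 0.799. With 17% drop-out, 656/0.83 = 790.4 (stated 790). This reproduces and does not depend on the definition of pregnancy.

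**The two rules side by side, months 4–6**

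| Result after a positive urine test | 5.7.5 | 7.2 as written |
|---|---|---|
| B: serum below 5 | no pregnancy, next cycle | pregnancy |
| C: serum above 5, not rising | no pregnancy, next cycle | pregnancy |
| D: above 5 and rising | pregnancy, ultrasound | pregnancy |

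**Inputs for the size**

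- Control live births, from 7.3: "assuming 5% live birth rate in the first 3 months of timed intercourse and a 20% live birth rate in the 3 clomid/IUI cycles", so 0.05 + 0.20 = 0.25.
- N = 395 per arm, from 7.3.
- L, the share of home positives ending without live birth: assumed 0.20 to 0.35, equal in both phases.
- u, the share of months 4–6 home positives that are B or C: assumed 0.05 to 0.20.

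**Simple model (each home positive is a separate couple)**

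- Rate under 7.2 = 0.25/(1 − L)
- B/C events = u × 0.20/(1 − L)
- Rate without B/C = the difference

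| L, u | Under 7.2 | Without B/C | Gap, points | Couples of 395 |
|---|---|---|---|---|
| 0.20, 0.05 | 31.25% | 30.00% | 1.25 | 4.9 |
| 0.25, 0.10 | 33.33% | 30.67% | 2.67 | 10.5 |
| 0.35, 0.20 | 38.46% | 32.31% | 6.15 | 24.3 |

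**Allowing a B/C couple to conceive in a later IUI cycle.** Such a couple may count under both rules, so the gap per couple is smaller. Let D = 0.20(1 − u)/(1 − L) be the cumulative confirmed rate over three cycles. The per-cycle confirmed rate is d = 1 − (1 − D)^(1/3), and the per-cycle B/C rate is b = d × u/(1 − u). The share ever home-positive is 1 − (1 − d − b)³, and the gap is that share minus D.

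- Low: D = 23.75%, d = 0.0864, b = 0.0045, ever positive 24.88%. Gap 1.13 points (4.5 couples).
- Middle: gap 2.40 points (9.5 couples).
- High: D = 24.62%, d = 0.0899, b = 0.0225, ever positive 30.06%. Gap 5.45 points (21.5 couples).

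**Miscarriage rate: direction only.** Let P be pregnancies without B/C, M their losses and E the B/C events, with M smaller than P. If B/C events are recorded as losses, the rate is (M + E)/(P + E), which exceeds M/P. If they enter only the denominator, it is M/(P + E), which is below M/P. The plan does not say which applies.

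**The case against.** The strongest defence is that the home test is the only measure written for all six months. Section 7.2 therefore gives one uniform rule, whereas adding the serum result changes the event definition at month 4, inside the hazard model. That cost is real and equal in both arms. It argues for reporting both definitions, but it does not make a case that the protocol classes as no pregnancy a good primary reading of the pregnancy rate.

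A second objection also stands in part. A detectable level that does not rise (C) does not exclude a very early failed conception, so these cases should be described as classed by the protocol as no pregnancy, and not as proven non-pregnancies.

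Third, clinical pregnancy with cardiac activity is already a confirmed secondary outcome. That limits the consequence but does not repair the pregnancy rate or time to pregnancy.

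A reader might infer that the miscarriage rate must be overstated. The documents do not support that. In months 4–6 only D couples go on to the ultrasound, which 6.9 names as a source of the miscarriage estimate, and 5.7.9 collects miscarriage as a pregnancy outcome. B and C couples start another cycle, and nothing directs that they be recorded as losses.

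A reader might also infer that live births are missed after a loss, because visit 4 includes the item "Confirm pregnancy status (pregnant or not pregnant) of female partner" and yet the protocol says "Instruct male to come to pregnancy ultrasound visit to complete study visit 4". That instruction sits under result D of the IUI cycles, and no text moves visit 4 for conceptions in months 1–3. Section 5.7.7 ends only the intervention phase after a loss, and no passage cancels later follow-up.

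**Conclusion.** The conflict is in the current text and nothing reconciles it. Followed as written, 2.8 and 7.2 count B and C cases as pregnancies and stop time to pregnancy at that cycle. On the assumed ranges for L and u, the control pregnancy rate is inflated by about 1 to 6 points (1.1 to 5.4 per couple if later conception is allowed). Neither range comes from the documents, so the true size is unknown. No figure is claimed for the miscarriage rate, whose direction is open.

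A reader might go further and infer bias between arms or lost power. The same tests and the same rule apply in both arms, so no between-arm bias is built in. The plan states no power or expected rates for the pregnancy outcome, so no loss is claimed. Live birth, clinical pregnancy and the 790 sizing are untouched. The point is minor, confined to secondary outcomes, and worth settling before analysis.

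**What to change.** Amend 2.8, 4.2 and 7.2 to state:

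- A positive home test counts as a pregnancy unless a serum hCG obtained under 5.7.5 is below 5 mIU/ml or does not rise.
- Where no serum result exists, the home test stands.
- B and C couples remain at risk in the time-to-pregnancy model.
- B and C events enter neither the numerator nor the denominator of the miscarriage rate.
- The all-home-test definition is reported as a sensitivity analysis, because some C cases may be very early losses.

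The cost is wording in three sections and one extra analysis on serum results that 5.7.5 already obtains. No new draw, visit or contact is needed. The remaining downside is that positives are serum-checked in months 4–6 but not in months 1–3, equally in both arms. The report should say so.
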